6.6. Baseline Definition

Unless otherwise specified, the following general principles apply for determining the baseline for daily diary variables and for variables collected during scheduled visits:

Primary endpoint parameter rTNSS

The baseline will be defined as the average of the last 8 consecutive AM and PM assessments during the last 4 days of the run-in period from the Day -4 PM assessment to the AM assessment on the day of randomization. At least 6 out of 8 reading scores should be available in order to calculate baseline score.

Secondary and other 12-hour average AM and PM endpoint parameters

The same method will be used to determine the baseline for secondary and other 12-hour average AM and PM efficacy endpoint parameters:

- average AM and PM rTNSS, iTNSS, and corresponding AM and PM individual symptoms
- average AM and PM rTOSS; average AM and PM iTOSS
- average AM and PM rTNNSS, average AM and PM iTNNSS and corresponding individual symptoms

Other endpoints for AM or PM nasal/non-nasal symptoms

The baseline score will be defined as the average of the last 4 consecutive AM or PM assessments (respectively for either AM or PM corresponding endpoint) during the last 4 days of the run-in period from the Day -4 PM assessment to the AM assessment on the day of randomization. At least 3 out of 4 reading scores should be available in order to calculate baseline score.

Safety endpoints

Unless otherwise specified, 'baseline' for safety analysis will be defined as the last available assessment prior to the first dose of study drug following randomization.

PRQLQ and PNSS

Baseline is defined as the score at the Randomization Visit (Day 1; Visit 2).

6.7. Derived and Transformed Data

6.7.1. Baseline Age

Age is the subject's age in years calculated based on the informed consent date and subject's date of birth.

If the month and day of informed consent is on or after the month and day of birth:

$$\text{Age} = \text{year of informed consent} - \text{year of birth}$$

If the month and day of informed consent is before the month and day of birth:

Age = year of informed consent – year of birth – 1

6.7.2. Study Day

If the date of interest occurs on or after the randomization date:

Study day = date of interest – randomization date + 1

If the date of interest occurs before the randomization date:

Study day = date of interest – randomization date

There is no study day 0.

6.7.3. Change from Baseline

Change from baseline in average AM and PM 12-hour rTNSS over a 14-day treatment period

- For mixed-effect model repeated measures (MMRM) model, this will be derived by calculating a mean score for each subject, based on the post-dose PM of the dosing day and AM assessment of next day for each day (ie Day 1 measurement = Average of the PM assessment on Day 1 and AM assessment of Day 2 and so on).
- For Analysis of Covariance (ANCOVA) model, the overall mean change from baseline over the 14 day period includes assessment from Day 1 PM assessment through Day 15 in the morning.

The same derivation method will be applied to endpoint change from baseline in average AM and PM 12-hour for iTNSS, rTOSS, iTNSS, rTNSS, iTNSS, individual reflective/instantaneous nasal/non-nasal symptom scores.

For all other endpoints, change from baseline is calculated as the difference between the post-baseline result and the baseline result.

Percent change is calculated as (change from baseline / baseline result * 100).

6.7.4. Visit Windows

Subject participation may be 22 days up to 27 days with 7 to 10 days of a screening/run-in period and a 14-day treatment period, with allowable window periods for the study visits. The following visit windows are permitted: ± 2 days for the Treatment Visit (Visit 3) and ± 2 days for the Final Visit/Discontinuation Visit (Visit 4). However, only data up to Day 15 AM is to be included in the efficacy analysis of subject-reported nasal and non-nasal symptoms.

Table 2: Visit Windows (Days)

Visit	Relative Target Day	Visit Window
Visit 1 (Screening)	-7	-10 – -7
Visit 2 (Randomization)	1	1
Visit 3 (Treatment)	8	6 – 10
Visit 4 (Final/Discontinuation)	15	15 – 17

6.7.5. Unscheduled Visits

An unscheduled visit (or telephone follow-up) may be performed at any time during the study at the subject's request or as deemed necessary by the Investigator. The date and reason for the unscheduled visit will be recorded on the CRF/eCRF as well as any other data obtained (eg, AEs, concomitant medications/treatments, and results from procedures or tests).

Data collected at unscheduled visits will be included in the listings, but not in the summary tables.

6.8. Handling of Missing Data

6.8.1. Missing Efficacy Endpoints

- Change from baseline in average AM and PM 12-hour rTNSS over a 14-day treatment period: For mixed-effect model repeated measures (MMRM) model if an AM or PM measurement is missing then the non-missing AM or PM measurement is used as the mean response for that day. If both the AM and PM measurement is missing then the mean response for that day will be missing.

The same methodology will be applied to endpoints of change from baseline in average AM and PM 12-hour iTNSS, rTOSS, iTTOSS, rTNNSS, iTNNSS, individual reflective/ instantaneous nasal/non-nasal symptom scores.

- If either the baseline or the post-baseline result is missing, the change from baseline and percent change are also set to missing.

6.8.2. Missing Start and Stop Dates for Prior and Concomitant Medication

- See section 9.4.

6.8.3. Missing Start and Stop Dates for Adverse Events

- See section 9.2.

7. STUDY POPULATION

The study population analyses will be based on the safety analysis set, unless otherwise specified. Table 3 provides an overview of the planned study population analyses.

Table 3: Overview of Planned Study Population Analyses

Display Type	Data Displays Generated		
	Table	Figure	Listing
Subject disposition			
Total screened	Y[1]		
Treated with study medication during run-in period	Y[1]		
Randomized	Y[2]		
Study completion/withdrawal	Y[2]		Y
Reason for early termination	Y[2]		Y
Protocol Deviations			
Protocol deviations during randomized treatment period	Y[2]		Y
Protocol deviations during run-in period	Y[2]		Y
Protocol deviations during pre-run-in period	Y[1]		Y
Major protocol deviations	Y[2]		Y[4]
Subjects included in /excluded from analysis populations			
Summary of subjects in analysis population	Y[2]		
Subjects excluded from each analysis populations			Y
Subjects who withdrew due to inclusion/exclusion criteria with criteria number and description			Y
Demographic and Baseline Characteristics			
Demographic Characteristics	Y[3]		Y
Skin Prick Test/Allergy Testing			Y
Medical History			Y
Exposure and Treatment and Diary Compliance			
Exposure during randomized treatment period	Y[2]		Y
Treatment Compliance during randomized treatment period	Y[2]		Y
Diary Compliance			Y
Concomitant Medications			
Prior Medications			Y
Concomitant Medications during randomized treatment period			Y
Concomitant Medications during run-in period			Y
Pollen Count and Rain Data			
Pollen and rain count listing by site			Y

NOTES :

- Y = Yes display generated
- [1]: Data from clinic or database
- [2]: Display will be based on the SAS

Display Type	Data Displays Generated		
	Table	Figure	Listing

- [3]: Display will be based on the SAS population and repeated for the FAS and PPS populations
- [4]: Major protocol deviations will be included in the listings of all protocol deviations.

7.1. Subjects Disposition

The subject accountability and disposition information will be summarized by study treatment group. The number of subjects screened, treated with study medication during the run-in period, randomized, treated with study medication following randomization, and the number of subjects in each analysis set will be tabulated. In addition, completion status and primary reason for withdrawal will be summarized by study treatment group.

7.2. Protocol Deviations

Important protocol deviations (PDs) will be listed and summarized by study treatment group, separately for pre-run-in, run-in and randomized treatment periods. Major deviations will lead to patients being excluded from the per-protocol analysis set as defined in Section 6.5.3. Major protocol deviations will be listed and discussed in the CSR.

7.3. Demographic and Baseline Characteristics

Subject demographic information will be collected at the Screening Visit (Visit 1). Demographic information includes age sex, race/ethnicity, will be summarized by treatment group separately for the SAS, FAS, and PPS analysis set. Other baseline characteristics including allergen test will be displayed in listing.

Continuous variables such as age will be summarized using descriptive statistics (number of subjects, mean, standard deviation, median, minimum and maximum). Categorical variables such as sex and race will be summarized using frequencies and percentage.

All data will be listed by treatment and subject.

7.4. Listing of Subject Inclusion and Exclusion Criteria

All patients who failed any inclusion/exclusion criteria will be listed along with details of the failed criteria.

Failed inclusion/exclusion data will be listed by treatment and subject.

7.5. Medical History and Medical Conditions Present at Entry

All relevant medical and surgical history and current medical conditions will be recorded at the Screening Visit (Visit 1).

Medical history data will be listed by treatment and subject.

7.6. Prior Medication History and Medications Present at Entry

At Visit 1 subjects will be questioned about prior medication history and medications present at entry. Prior medications are defined as medications that started and ended before the first administration of the study medication.

All prior medications taken will be listed by treatment and subject.

7.7. Baseline Physical Examination

Physical examinations (comprehensive) will be performed at the Screening Visit (Visit 1).

Descriptive statistics (frequency and percentage) will be used to summarize physical examination results by body system, treatment group and visit. In addition, the number of subjects with values of potential clinical significance determined by the investigator will be tabulated.

All physical examination data will be listed by treatment and subject.

7.8. Baseline Vital Signs

The subject's baseline vital signs will be recorded (pulse rates, sitting systolic and diastolic blood pressure, height and weight) at Randomization Visit (Visit 2). Descriptive statistics (number of subjects, mean, standard deviation, median, minimum and maximum) will be used to summarize vital sign results by treatment group and visit.

Values outside the respective normal range and values deemed as clinically significant by the Investigator will be listed.

The number of subjects with values of potential clinical significance determined by the investigator will be tabulated by treatment group and visit.

7.9. Baseline Focused ENT/Eye examination

The subject's baseline focused ENT/Eye examinations will be performed at Randomization Visit (Visit 2). Descriptive statistics (frequency and percentage) will be used to summarize ENT/Eye examination results by treatment. In addition, the number of subjects with values of potential clinical significance determined by the investigator will be tabulated.

All ENT/Eye examination data will be listed by treatment and subject.

7.10. Baseline Efficacy Evaluations

Descriptive statistics (number of subjects, mean, standard deviation, median, minimum and maximum) will be summarized by treatment group for the following:

- Baseline average (AM/PM), AM and PM subject-reported rTNSS, iTNSS, rTOSS, iTOSS, rTNNSS and iTNNSS.

- Baseline average (AM/PM), AM and PM reflective individual nasal symptoms, instantaneous individual nasal symptoms, reflective individual non-nasal symptoms and instantaneous individual non-nasal symptoms.
- PRQLQ, PNSS.
- Individual PRQLQ scores and individual PNSS symptom scores.

8. EFFICACY

The primary efficacy analysis of the primary efficacy endpoint will be performed on both the FAS (primary) and the PPS (supportive).

Table 4: Overview of Efficacy Analysis of the Primary Endpoint

	Stats Analysis		Summary		Individual
	T	F	T	F	L
Primary Endpoint: Change from Baseline in Average AM and PM 12-hour rTNSS over a 14-day Treatment Period					
Primary analysis method: (MMRM Approach)					
rTNSS – MMRM– FAS	Y	Y	Y		Y
rTNSS – MMRM – PPS	Y	Y	Y		Y

NOTES :

- T = Table, F = Figure, L = Listing, Y = Yes display generated.
- Stats Analysis = Represents TF related to any formal statistical analyses (i.e. modeling) conducted.
- Summary = Represents TF related to summaries (i.e. descriptive statistics) of the baseline, post-treatment and change from baseline for the primary efficacy analyses method.
- Individual = Represents L related to any displays of individual subject observed raw data as well as post-baseline and change from baseline presented on the SAS dataset.

8.1. General Considerations

All tests will be 2-sided and at 5% level of significance unless otherwise stated.

In addition to the analyses described below, all variables will be summarized descriptively, as appropriate.

The primary goal of the analysis of the primary endpoint will be to assess the superiority of GSP 301 NS vs placebo NS treatment comparisons for the primary endpoint rTNSS.

The primary analysis will use the FAS and a supportive analysis will be based on the PPS. The interpretation of results from statistical tests will be based on the FAS. The PPS will be used to assess the robustness of the results from the statistical tests based on the FAS.

Unless otherwise stated, 'treatment' refers to treatment group as randomized, rather than based on the actual treatment received.

8.2. Statement of the Null and Alternate Hypotheses

The primary endpoint is the change from baseline in average AM and PM subject-reported 12-hour rTNSS over the 14-day treatment period.

A significance test will be made for the primary endpoint in order to assess for superiority of GSP 301 NS versus placebo NS. Demonstration of superiority for this treatment comparison will be based on a hypothesis testing approach, whereby the null hypothesis is that there is no difference between treatment groups and the alternative hypothesis is that there is a difference between the treatment groups.

A 2-sided 5% risk associated with incorrectly rejecting the null hypothesis (significance level) is considered acceptable for this study.

8.3. Subgroup Analyses

The following subgroups of clinical interest will also be summarized for the FAS only, by treatment group and by day, for rTNSS: age group (6-<9, 9-<12), gender (female/male), race (American Indian or Alaska Native, Asian, Black/African American, Other and White) and ethnicity (Hispanic or Latino and Not Hispanic or Latino). iTNSS, rTOSS and PRQLQ will be analyzed only for the age subgroups (6-<9, 9-<12).

Descriptive statistics (number of subjects, mean, standard deviation, median, minimum and maximum) will be provided for baseline, post treatment and change from baseline.

Also, the MMRM analysis of rTNSS will be repeated for each of the age subgroups (6-<9, 9-<12).

Further subgroup analyses might be performed on an ad-hoc basis if deemed necessary.

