13.1. Sample Size

A sample size of 382 evaluable subjects, allocated 1:1, will provide 90% power to detect a between-group mean difference (GSP 301 NS vs placebo NS) of 1.0 in the absolute change from baseline in average AM and PM subject-reported 12-hour rTNSS over a 14-day treatment period (assuming a 2-sided alpha of 5%). A standard deviation of 3.0 in the change from baseline in 12-hour rTNSS over a 14-day treatment period has been assumed. Assuming a drop-out rate of 15%, a total of approximately 450 subjects are planned to be randomized (225 subjects in each treatment group). Depending on the actual drop-out rate, the Sponsor may decide to randomize higher or lower number of subjects in order to meet the required sample size of 382 evaluable subjects.

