8.5. Analysis of the Primary Efficacy Endpoint

8.5.1. Primary Efficacy Analysis

The primary endpoint, change from baseline in average AM and PM subject-reported 12-hour rTNSS over a 14-day treatment period, will be evaluated using a mixed-effect repeated measures (MMRM) model. The model will adjust for study treatment, site, baseline 12-hour rTNSS and study day as the within-subject effect, with the assumption that any missing data is missing at random (MAR).

The interactions of site-by-treatment and baseline-by-treatment will be investigated separately using two independent models and will only be included in the final model if they are statistically significant at the alpha=5% level. In order to determine the interaction/s to be included in the final model, the following model-fitting process will be followed:

1. The main-effects model containing study treatment, site, baseline 12-hour rTNSS and study day will be fitted first:
 - a. Unstructured covariance will initially be assumed.
 - b. If the model does not converge using the unstructured covariance structure, the autoregressive (order 1) AR(1) structure will be used.
 - c. If the AR(1) structure also does not converge, other covariance structures deemed appropriate to fit the data will be used.
2. Two independent models will be fitted using the covariance structure of the model that converged in step 1: one model containing the site-by-treatment interaction and the other model containing the baseline-by-treatment interaction. If the interaction term is significant, it will be included in the final model. If convergence is not obtained after adding both of the interaction terms (if both are significant), the more significant interaction term will be kept in the model. Any interaction term that make model not converge will not be added to the final model.

The statements of a SAS® PROC MIXED analysis would be (if the interactions of treatment*baseline and treatment*site are not statistically significant):

```
PROC MIXED;
CLASS subject treatment site day;
MODEL change = treatment site baseline day;
REPEATED day / SUBJECT = subject TYPE=UN;
LSMEANS treatment / CL DIFF E ;
ODS OUTPUT LSMEANS=lsmeans ;
ODS OUTPUT DIFFS=diffs ;
RUN ;
QUIT ;
```

The adjusted means for each treatment and the estimated treatment differences for the treatment comparisons will be presented together with 95% confidence intervals for the differences and p-

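### The age-group analysis uses two separate MMRMs and specifies no treatment-by-age contrast; separately, each subgroup's 95% CI is modestly too narrow

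*SAP*

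**What the plan says.** SAP 8.3 makes age the only subgroup factor with a modelled treatment effect: "the MMRM analysis of rTNSS will be repeated for each of the age subgroups". Sex, race and ethnicity get descriptive summaries. The model carried over from SAP 8.5.1 has treatment, site, baseline and day. The only interactions screened in it are site-by-treatment and baseline-by-treatment, each kept if significant at 5%. The covariance starts as unstructured, with a fallback: "If the model does not converge using the unstructured covariance structure, the autoregressive (order 1) AR(1) structure will be used". The SAS statements shown there name no degrees-of-freedom or small-sample option.

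The shell for Table 14.2.1.6 uses the same terms. It shows an LS mean difference, its standard error, a 95% CI and a p-value for the younger group, overall and for Days 1 to 14, and is then repeated for the older group. Neither the SAP, its shells nor the protocol contains a treatment-by-age term, test or between-age estimate. Protocol 13.7 says only that efficacy within age and other subgroups will be looked at, and leaves detail to the SAP.

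**The concern.** There are two distinct issues.

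The first is the missing comparison. The table will hold 30 treatment p-values (15 per age group) and no estimate of how far the two age effects differ. If one group crosses 0.05 and the other does not, the natural but wrong reading is that the drug works at one age and not the other. The fits may also differ in form, because the covariance fallback and the interaction screen would run separately in each.

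The second is interval width. Each subgroup fit re-estimates every site effect and the whole 14-day covariance from about half the children. Treating that estimated covariance as known makes the standard error too small, and more so as the sample shrinks.

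**Working it through.** **The plan's own figure.** Inputs from Protocol 13.1: difference 1.0, SD 3.0, two-sided alpha 0.05, 90% power, "A sample size of 382 evaluable subjects, allocated 1:1". Per arm, n = 2(1.960 + 1.282)² × 3.0² / 1.0² = 189.2, so 190 per arm and 380 in total, against 382 stated. At 191 per arm, SE = 3.0√(2/191) = 0.307 and power = Φ(1.0/0.307 − 1.960) = 90.3%. Inflating for drop-out, 382/0.85 = 449.4, so 450. The plan's figures reproduce.

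**Precision by age group.** SE_g = 3.0√(4/N_g), half-width = 1.960 × SE_g, power for a true effect of 1.0 = Φ(1.0/SE_g − 1.960). The age split is not in the documents, so a range is shown at N = 382.

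| Split | SE | Half-width | Power for 1.0 |
|---|---|---|---|
| 50/50 | 0.434 each | 0.851 each | 63% each |
| 40/60 | 0.485, 0.396 | 0.951, 0.777 | 54%, 71% |
| 30/70 | 0.560, 0.367 | 1.099, 0.719 | 43%, 78% |

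**Chance of discordant p-values when the true effect is 1.0 in both groups.** P = p₁(1 − p₂) + p₂(1 − p₁). At 50/50 this is 2 × 0.634 × 0.366 = 46%; at 40/60 it is 48%; at 30/70 it is 54%. With all 450 children the range is 42% to 51%.

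**The missing contrast.** The groups are different children, so SE = √(SE₁² + SE₂²). At 50/50 this is 0.614, half-width 1.20, power 37% for an age difference of 1.0; 90% power needs (1.960 + 1.282) × 0.614 = 1.99. At 40/60 the half-width is 1.23 (power 36%), and at 30/70 it is 1.31 (32%). With 450 children at 50/50 the half-width is 1.11 (42%).

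**Does separate fitting by itself make the intervals too narrow?** No. With one averaged outcome per child and 191 per age group (5,000 simulated trials, SD 3.0), the separate-fit 95% CIs covered 95.0% and 94.8%.

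**Does the SAP's 14-day model?** Yes, modestly. The unstructured matrix has 14 × 15 / 2 = 105 parameters. The model was simulated under the null with complete data, an assumed within-child correlation, 30 assumed sites and no small-sample correction, 4,000 trials per row (Monte Carlo error near 7%: √(0.07 × 0.93/4000) = 0.4 points).

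| Children in the fit | Type I error | SE too small by |
|---|---|---|
| 382 | 5.9% | 4% |
| 225 | 6.1% | 6% |
| 191 | 7.4% | 8% |
| 153 | 8.2% | 12% |
| 115 | 9.7% | 15% |

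A run of 12,000 trials gave 6.65% at 225 and 7.16% at 191. At 191 children, 15 and 45 sites gave 7.8% and 7.2%. In a further run at 191 with 15 sites, the mean model SE was 0.427 against an empirical SD of 0.471, a ratio of 0.906, so about 9% too small. The last two rows of the table correspond to the smaller group under 40/60 and 30/70 splits of 382.

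**Would pooling the age groups help?** In one joint fit, type I error was about 6% and SEs were 4-5% too small. That assumes equal variances. With SDs of 3.5 and 2.5 and one averaged outcome per child, a common-variance joint model covered 90.7% and 98.6%, against 94.7% and 95.6% for separate fits. In the 14-day model the corresponding joint type I errors were about 10% and 2%.

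**The case against.** The protocol promises efficacy within subgroups, not a comparison between them, and a separate fit does answer whether an effect is seen in the younger children. SAP 8.4 limits formal testing to the primary and three secondary endpoints, so no subgroup claim is licensed. The shell shows differences, SEs and CIs beside the p-values, and footnotes any interaction that enters. Nothing in the documents suggests that either subgroup will fail to converge. All of that stands, and it keeps this an exploratory reporting matter.

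Three stronger readings are tempting and are not supported:

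- A reader might infer that the plan makes the comparison impossible. It does not. The shell reports a difference and SE for two disjoint groups, so the contrast can be formed afterwards (simulated coverage 94.8% with one averaged outcome per child). It is unspecified, not unobtainable.
- A reader might infer that the missing interaction, or separate fitting as such, makes the intervals too narrow. The averaged-outcome check shows otherwise. The cause is the uncorrected covariance estimate, which also touches the primary model; splitting by age makes it worse.
- A reader might take too narrow to mean narrower than the full-set interval. At an even split the subgroup interval is 0.851/0.602 = 1.41 times as wide. It is too narrow only against its nominal 95% coverage.

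The objection that a pooled model can do harm also stands where variances differ by age, and the fix has to allow for it.

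**Conclusion.** The concern holds in two separate parts, both minor. First, the plan gives two age-specific effects and no direct inference on their difference, while discordant p-values would arise in about 46-54% of trials even if the true effect were 1.0 at both ages. This rests on N = 382, SD 3.0 and age splits from 50/50 to 30/70. Second, at 191 to 225 children the subgroup CIs are modestly too narrow, with type I error about 7% and SEs about 6-9% too small. This rests on assumed site count, age split and correlation, and on complete data; an uneven split makes it worse for the smaller group. Neither part affects a confirmatory conclusion. Different covariance structures or model terms in the two fits are a possibility that the rules permit, not a predicted event.

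**What to change.** Pre-specify one FAS MMRM for rTNSS that adds age group and treatment-by-age-group to the SAP 8.5.1 terms. Report the interaction estimate with its 95% CI, labelled exploratory. Use DDFM=KR (Kenward-Roger) in this model and in any age-specific fit. Require the same model terms and the same covariance structure in both age groups, so that a fallback or a retained interaction in one applies to the other. For the age-specific effects, either let the covariance differ by age group within the joint model or keep the separate fits.

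The cost is two model terms, one SAS option and one table row. The downsides are that pooling assumes common site effects, and a common covariance unless it is allowed to differ, and that the contrast will be imprecise, with a half-width of about 1.2 at N = 382. That imprecision is itself a reason to show the interval. The simulations did not include Kenward-Roger, so the size of its improvement is not quantified here.
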